## **2.4 Compliance Statement**

This study will be conducted in full accordance all applicable Children's Hospital of Pittsburgh and University of Pittsburgh Research Policies and Procedures and all applicable Federal and state laws and regulations including 45 CFR 46. All episodes of noncompliance will be documented.

The investigators will perform the study in accordance with this protocol, will obtain consent and assent, and will report unanticipated problems involving risks to subjects or others in accordance with institutional Policies and Procedures and all federal requirements. Collection, recording, and reporting of data will be accurate and will ensure the privacy, health, and welfare of research subjects during and after the study.

## **3 STUDY OBJECTIVES**

The purpose of the study is to determine the feasibility and acceptability of CGM-based at-home glucose challenge as an alternative to clinical OGTT for T2D risk assessment in youth.

### **3.1 Primary Objective**

The primary objective is to determine the feasibility of at-home CGM-based glycemia evaluation as measured by adequacy of CGM data capture and nutrition logging quality and completion.

### **3.2 Secondary Objectives**

The secondary objectives are to:

---

- determine the test performance characteristics of at-home, CGM-measured glucose challenge as compared to a gold-standard laboratory-based 2-hour OGTT
- to determine the acceptability of use of CGM for at-home dysglycemia evaluation as an alternative to clinical 2-hour OGTT

## 4 INVESTIGATIONAL PLAN

### 4.1 General Schema of Study Design

This prospective observational study will include screening by phone or in-person, completion of one in-person study visit, completion of 10 days of CGM wear and survey completion at home, one at-home glucose challenge and one at-home mixed meal challenge, and one phone interview.

#### 4.1.1 Screening Phase

Potential subjects will be identified through weekly review of Pediatric Endocrinology and Diabetes clinic schedules. In addition, a list of potentially eligible patients will be generated via review of a list of patients with diagnosis of prediabetes or obesity and insulin resistance from current and previous research conducted by the PI or the PI's mentor, [name]. The Wellness and Obesity Registry, monitored by [name], will be used to screen for potential subjects as well. The CAYAH RESEARCH INTEREST FORM will also be used for recruitment purposes. This is a REDCap form with a survey link that will contain questions for adolescents to answer self-screen questions which are non-sensitive. Center for Adolescent and Young Adult Health (CAYAH) clinical staff will manage and distribute this survey. CAYAH clinical research staff will advertise the study to the teen. If the teen (age 13 or older) indicates interest in the study by viewing the study advertisement within the CAYAH RESEARCH INTEREST FORM, they will provide their contact information to the CAYAH clinical research staff who will then share it with the study team. Medical records of potential subjects will be screened by the study team using the protocol inclusion and exclusion criteria. Those who appear to meet the criteria will be approached by a member of the study team by phone, email, or in-person and asked if they would like to hear about the study. Subjects and/or their parent/guardian will provide demographic, social, and medical information about themselves, their child, or family (as applicable) to confirm eligibility.

#### 4.1.2 Study Visit

After study procedures are reviewed and questions answered, written informed consent and assent (participants<18) will be obtained if not already obtained electronically via REDCap. Participants will arrive after overnight fast (minimum 10 hours) and will undergo physical examination by a pediatric endocrinologist as well as anthropometrics, vital sign measurement, questionnaires (medical, family, social history), and 2-hour OGTT performed according to American Diabetes Association criteria.(American Diabetes Association Professional Practice, American Diabetes Association Professional Practice et al. 2022) After baseline (time 0) venous blood sample, participants will ingest glucose solution (1.75 g/kg body weight, max 75g) within 5 minutes or less. Additional venous blood samples will be obtained at timed intervals after ingestion to determine plasma glucose, insulin, and c-peptide

(30, 60, 90, 120 min) . HbA1c will also be measured (one venous blood sample). During OGTT, Dexcom G6 Pro (blinded, no data visible to participant) CGM will be placed on the participant's abdomen by study staff trained in CGM placement. Participants will be assigned a unique study ID for use with Dexcom and survey collection. Participants (or their parent if the participant does not have a phone with text messaging capability) will also be registered for text message-based surveys via Mosio, a text messaging platform for clinical research, and will be instructed on nutrition, activity, and sleep logging to be completed during the 10-day CGM wear period. Paper logbooks will be provided for use in case of technical difficulties with texts. Participants will be provided with a wrist-worn actigraphy device (ActiGraph GT9X Link) to wear continuously during the 10-day period for collection of objectively measured activity and sleep data to define periods of eating, overnight fasting, and exercise.

#### 4.1.3 Observation Period

Participants will be instructed to participate in their typical daily routines, with the exception of two at-home challenges: 1) glucose, and 2) mixed-meal. The ***at-home glucose challenge*** will serve as the primary comparison to the laboratory-measured OGTT. For this challenge, participants will be asked to drink the same glucose solution (Trutol) consumed as part of the OGTT at PCTRCC and provided with the appropriate weight-based amount. They will be instructed to choose a day between days 3 and 9 of the study period during which they will be able to fast for at least 10 hours, drink the glucose beverage, and then be inactive for 2 hours. They will log the date and time of glucose ingestion. For the ***at-home mixed-meal challenge***, participants will be asked to choose a day between study days 3 and 9, separate from the glucose challenge day, during which they will be able to fast for at least 10 hours, eat a snack or meal with at least 50 grams of carbohydrate as well as fat and protein content, and then be inactive for 2 hours. All participants and families will be instructed on determination of carbohydrate content using example foods that they typically consume. Participants will receive \$20 for travel to the study visit, loaded onto a university payment card.

***Text message-based surveys and actigraphy:*** Participants will be sent surveys 3 times daily via text message, inquiring about food and drink intake, physical activity, and time in bed (start/stop times). Survey responses will be collected via Mosio and entered in Research Electronic Data Capture (REDCap), a secure, web-based application for clinical research data collection. Branching logic will be used in REDCap so that participants will only need to provide detail for relevant activities each time. As an incentive for ActiGraph wear, participants will earn an additional \$20 if the ActiGraph device is worn for at least 8/10 days.

***Study completion:*** On day 10 of CGM wear (or earlier in case of discomfort), participants will remove the sensor and transmitter at home by simply peeling off the device. Transmitter and ActiGraph will be returned to the study team by participants using prepaid shipping envelopes or in-person if preferred. Upon receipt of the transmitter and ActiGraph, participants will receive compensation for participation in the study (\$100).

#### 4.1.4 Individual Interview and Disordered Eating Questionnaire

Upon completion of CGM wear, youth participants, with or without their parents at the discretion of the research team, will be invited to participate in a 20-minute semi-structured interview via phone or videoconferencing platform to assess the acceptability of CGM use as an alternative to clinical OGTT for diabetes risk assessment. Interviews will also be used

to elicit barriers and facilitators to diabetes evaluation and follow up for diabetes risk. Interviews will be conducted by study staff and will be audio-recorded and professionally transcribed.

After completion of the interview, participants will be asked to complete a brief, 12-item questionnaire related to disordered eating behaviors in the past 28 days. This will be completed via REDCap. Participants will be allowed to skip questions if they are uncomfortable answering.

Participants will be compensated \$15 for completion of the interview.

#### **4.1.5 Data Collection**

*CGM data extraction:* Upon receipt of a participant transmitter, study staff will use a Dexcom G6 Pro receiver to upload the data to Clarity, a cloud-based software for data visualization and extraction. Glucose values and timestamps will be downloaded via CSV file to the principal investigator's secure UPMC shared drive for analysis.

*Actigraphy data extraction:* ActiLife 6 desktop software will be used to extract actigraphy data from returned ActiGraph GT9X Link devices. Automatically-detected sleep periods will be cross-checked with participant-reported start/end times in bed.

### **4.2 Study Duration, Enrollment and Number of Sites**

#### **4.2.1 Duration of Subject Study Participation**

The study visit is expected to take approximately 2.5-3 hours. CGM will be worn for 10 days, beginning the day of the study visit. The phone interview is expected to take approximately 30 minutes. The phone call will take place no more than 4 weeks after the study visit.

#### **4.2.2 Total Number of Study Sites/Total Number of Subjects Projected**

This study will be conducted at the Children's Hospital of Pittsburgh. A maximum of 40 subjects will be included.

### **4.3 Study Population**

We will not restrict enrollment based on gender or age within the eligible age group.

We plan to enroll only English-speaking patients.

#### **4.3.1 Inclusion Criteria**

1. Any gender, age 8-18 years
2. Tanner 2 or higher pubertal development
3. Overweight or obese ( $BMI \geq 85^{\text{th}} \text{ percentile for age/sex}$ , or  $\geq 25 \text{ kg/m}^2$  for participants  $\geq 18$  years)
4. A) No previously documented abnormal HbA1c or glucose but at higher risk for T2D based on race/ethnicity (Black, Hispanic, Asian, Native American, Pacific Islander),

diagnosis with dyslipidemia, hypertension, polycystic ovary syndrome, presence of acanthosis nigricans, or first degree relative with T2D (n = 15); *or* B) previously documented (within 6 months) HbA1c 5.7-7.0%, fasting glucose  $\geq 100$  mg/dL, or 2-hour plasma glucose on OGTT of  $\geq 140$  mg/dL (n = 25)

5. Consent (adult subjects), parental/guardian permission (if applicable), assent (if applicable)
6. Willingness to wear ActiGraph watch and CGM continuously for 10 day study duration

#### **4.3.2 Exclusion Criteria**

1. Current or recent (within 1 month) use of diabetes- or obesity-related medication
2. Current use of hydroxyurea (due to interference with CGM)
3. Known type 1, cystic fibrosis-related, or medication-induced diabetes
4. Potential subject unable to speak or read in English
5. Severe cognitive impairment
6. Current or previous pregnancy

Subjects that do not meet all of the enrollment criteria may not be enrolled. Any violations of these criteria must be reported in accordance with IRB Policies and Procedures.

## **5 STUDY PROCEDURES**

### **5.1 Phone screening**

- Medical Record Review
- Brief study overview: 5 minutes
  - Consent/HIPAA Authorization: 5-10 minutes/as long as needed for full comprehension of study involvement (if not already obtained electronically via REDCap)
  - Screening questionnaire: 5 minutes
  - Overview of 12-hour overnight fast and upcoming study visit: 5 minutes

### **5.2 Study Visit**

- Vital signs (heart rate, blood pressure): 5 minutes
- Urine pregnancy test (all females): 3 minutes

- Height, weight, waist and hip circumference: 5 minutes
- Focused physical exam, including pubertal status: 5 minutes
- Fasting 2-hour oral glucose tolerance test: 120 minutes
  - Medical, surgical, family, social history: 10 minutes (during OGTT)
  - Provide ActiGraph device, instruct on use: 5 minutes (during OGTT)
  - Place CGM on abdomen, instruct on use: 5 minutes (during OGTT)
  - Review instructions for glucose and mixed meal challenge, including food label interpretation for carbohydrate content: 10 minutes (during OGTT)
  - Enroll in text messaging platform, instruct about survey completion: 5 minutes (during OGTT)
  - Provide addressed, pre-paid shipping envelope to return CGM, ActiGraph

### **5.3 Observation Period, Days 1-10**

#### **5.3.1 Non-Challenge Days:**

- Participant wears CGM, ActiGraph continuously
- Text messages sent 3 times daily (10 AM, 2 PM, 8 PM) to collect nutrition, physical activity, sleep records
- No changes to routine diet or activity

#### **5.3.2 Glucose Challenge: day of participant's choice between Days 3 and 9**

- Participant wears CGM, ActiGraph continuously
- After minimum 10 hours of fasting overnight, participant drinks study-provided glucose beverage without any additional food or drink and remains as inactive as possible for 2 hours
- Text messages sent 3 times daily (10 AM, 2 PM, 8 PM) to collect nutrition, physical activity, sleep records
  - At next available survey time, participant indicates time that glucose beverage was consumed (start and finish times)

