### 7.4 Statistical Methods

#### 7.4.1 Analysis of Primary and Secondary Outcomes of Interest

Primary objective: Determine the feasibility of at-home, CGM-based glycemia evaluation as measured by adequacy of CGM data capture and nutrition logging quality and completion on days of at-home glucose and mixed-meal challenge.

*H1a: Complete CGM data will be available for  $\geq 80\%$  of requested days worn:* The number of days with adequate CGM data will be divided by 9, omitting the first 24 hours due to possible inconsistent measurements after initial placement. Feasibility will be defined as  $\geq 80\%$  (7.2) of days with data.

*H1b: Documentation of glucose and mixed-meal challenge will be complete and adequate for analysis for  $\geq 80\%$  of participants:* The number of participants who document the date and time of glucose and mixed-meal ingestion (including mixed-meal content) will be determined and divided by the total number of participants. Feasibility will be defined as  $\geq 80\%$  of participants documenting date and time of either the glucose challenge, mixed-meal challenge, or both.

Secondary objective: Determine the test performance characteristics of at-home, CGM-measured glucose challenge with laboratory-based 2-hour OGTT.

*H2: CGM-measured glucose 2 hours and 5 minutes after standardized glucose ingestion will have adequate discrimination of normal ( $<140$  mg/dL) versus dysglycemic ( $\geq 140$  mg/dL) 2-hour OGTT glucose, as assessed by area under the receiver operating characteristic curve  $\geq 0.7$ :* Using participant logs via text message survey or paper-based logs, date and time of home glucose challenge will be determined and labeled in CGM data. A time point 2 hours and 5

---

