minutes later (accounting for lag due to interstitial measurement)(Wadwa, Laffel et al. 2018) (CGM-2h) will serve as the comparison to the 2-hour glucose during OGTT obtained at the study visit (OGTT-2h). Sensitivity, specificity, and positive and negative predictive values of CGM-2h to predict OGTT-2h $\geq$ 140 mg/dL will be assessed for various thresholds of CGM-2h. Area under the receiver operating characteristic curve (AUC) will be determined. An AUC threshold of  $\geq$ 0.7 will be used to define adequate discrimination. The same analysis will be repeated for the comparison of baseline CGM glucose (at time of glucose ingestion) to fasting glucose on OGTT, using a fasting glucose threshold of  $\geq$ 100 mg/dL to define dysglycemia. Finally, correlation analyses (Spearman or Pearson depending on distribution) will be performed to further explore the relationship between CGM indices obtained during at-home glucose challenge (e.g., baseline, peak, mean glucose) and both laboratory-measured HbA1c and plasma glucose during OGTT. Correlations will be examined across subgroups such as lower versus higher ActiGraph-measured physical activity level and self-reported carbohydrate intake on the day prior to at-home glucose challenge, age, pubertal stage, and body mass index.

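### The ingestion time that fixes CGM-2h and baseline CGM is self-reported at the next survey, minutes to about 4 hours after the drink, and is neither noted at the time nor checked

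*Combined protocol and SAP*

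**What the plan says.** On the challenge day, section 5.3.2 sets the survey times: "Text messages sent 3 times daily (10 AM, 2 PM, 8 PM) to collect nutrition, physical activity, sleep records". The drink comes first: "After minimum 10 hours of fasting overnight, participant drinks study-provided glucose beverage". No clock time is set for it. Its timing is then collected by survey: "At next available survey time, participant indicates time that glucose beverage was consumed (start and finish times".

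Section 7.4.1 uses that report in the analysis: "Using participant logs via text message survey or paper-based logs, date and time of home glucose challenge will be determined". The time is marked on the CGM trace, and two index values are read from it:

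- CGM-2h, defined in H2 as "CGM-measured glucose 2 hours and 5 minutes after standardized glucose ingestion". The extra 5 minutes allow for interstitial lag.
- The second comparison, "baseline CGM glucose (at time of glucose ingestion) to fasting glucose on OGTT".

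Elsewhere:

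- Section 4.1.3 says participants log when they took the glucose, but not that they do so while drinking.
- Section 4.1.2 provides paper logbooks for technical problems with texting.
- Section 4.1.5 cross-checks self-reported times for sleep only.
- Section 7.4.4 deals with gaps in the CGM trace, not with an uncertain time zero.

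**The concern.** The home challenge is the study's main comparison with the laboratory OGTT. The OGTT samples are drawn at timed intervals by staff, so an error in time zero falls on the home test alone. The plan corrects for a 5-minute lag on a device that reads every 5 minutes, yet leaves the start of the clock to an unchecked report that may come hours after the event.

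If the reported time is wrong, CGM-2h is read at the wrong point of the curve, and so is the baseline value. Error unrelated to the participant's true OGTT status adds noise to the index test and pulls the observed AUC toward 0.5. H2 is judged against an AUC of 0.7, so the loss bears on its conclusion. H1b would not reveal the problem, because it counts whether a date and time were documented, not whether they were right.

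**Working it through.** **Plan's own figure.** Section 7.5: 40 × (1 − 0.20) = 32 evaluable subjects. This reproduces and is not in dispute. The documents give no precision or power figure for the AUC.

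**Step 1: delay between drink and report.** Delay = next survey time − drink time. The survey times come from section 5.3.2; the drink times are assumed, as none is set.

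| Drink | Next survey | Delay |
|---|---|---|
| 6:00 | 10:00 | 4.0 h |
| 8:00 | 10:00 | 2.0 h |
| 9:30 | 10:00 | 0.5 h |
| 10:30 | 14:00 | 3.5 h |
| 12:00 | 14:00 | 2.0 h |

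With drinks spread evenly from 6 AM to noon, the mean delay is (4 × 2 + 2 × 3)/6 = 2.3 h. The share waiting at least 1 h is 5/6 = 83%, and at least 2 h is 4/6 = 67%. An 8 AM drink whose 10 AM survey is missed is reported at 2 PM, 6 h later.

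**Step 2: from minutes to mg/dL.** Error in CGM-2h = slope near 2 h × timing error. The slope is assumed to be 0.3 to 1.5 mg/dL/min. A 5-minute error then moves CGM-2h by 1.5-7.5 mg/dL, 15 minutes by 4.5-22.5, and 30 minutes by 9-45.

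**Step 3: effect on AUC.** Assumptions: OGTT-2h and error-free CGM-2h are bivariate normal, each with SD 35 mg/dL; mean OGTT-2h is 140, so the cutoff splits the sample in half; timing error is normal with mean zero; one slope applies to everyone. The attenuated correlation is

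ρ′ = ρ × 35 / √(35² + (slope × SD_t)²),

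and AUC is the mean of Φ(ρ′(|Z₁| + |Z₂|)/√(2(1 − ρ′²))) over independent standard normals Z₁ and Z₂. For ρ = 0.5, slope 1.0 and SD_t = 15: ρ′ = 17.5/√(1225 + 225) = 0.460, and AUC = 0.71.

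| ρ (error-free AUC) | Slope, mg/dL/min | SD 10 min | SD 15 min | SD 20 min |
|---|---|---|---|---|
| 0.5 (0.73) | 0.5 | 0.73 | 0.72 | 0.72 |
| | 1.0 | 0.72 | 0.71 | 0.70 (0.698) |
| | 1.5 | 0.71 | 0.69 | 0.67 |
| 0.7 (0.83) | 0.5 | 0.83 | 0.82 | 0.82 |
| | 1.0 | 0.82 | 0.80 | 0.78 |
| | 1.5 | 0.80 | 0.77 | 0.75 |

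A second model agrees in scale. With binormal classes and an assumed within-class SD of 25 mg/dL, AUC′ = Φ(z(0.75) × 25/√(25² + (slope × SD_t)²)). At slope 1.0, a true AUC of 0.75 becomes 0.746 at SD 5 min, 0.718 at 15 and 0.701 at 20.

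**Step 4: scale against sampling error.** Hanley-McNeil, AUC A = 0.73, 16 versus 16 (assumed split of 32): Q₁ = 0.73/1.27 = 0.575, Q₂ = 2 × 0.5329/1.73 = 0.616. Variance = [0.1971 + 15(0.575 − 0.533) + 15(0.616 − 0.533)]/256 = 0.0081, so SE = 0.09. The largest loss in the ρ = 0.5 block is 0.73 − 0.67 = 0.06. At A = 0.83 the same formula gives Q₁ = 0.709, Q₂ = 0.753 and SE = 0.07. There, only the worst case (0.83 − 0.75 = 0.08) exceeds one SE.

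**The case against.** The protocol fixes when the time is reported, not when it is noted. The drink is a planned, once-only event on a day the family chooses, after a fast and before 2 hours of inactivity that they must time themselves. Participants are also instructed on logging at the visit. Many may know the start time well. This stands as a reason to expect modest error, but nothing in the plan requires the time to be noted at once.

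Three stronger readings are tempting, and the documents do not support them:

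- A reader might infer that the time is always recalled from memory hours later. The delay can be minutes, and recall is an inference.
- A reader might infer that the text platform can already time-stamp the drink. Sections 4.1.2 and 9.1 show only that it sends and receives survey texts; unprompted messages and receipt times are not described.
- A reader might infer that timing error cannot be told apart from device error. A trace at 5-minute intervals after a 10-hour fast should show the rise after the drink, so gross errors could be found at analysis. The plan does not commit to that check.

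It is also fair that H2 is secondary in a feasibility pilot, and that whether families' ordinary logging is adequate is part of the primary question. A text sent by the participant can itself be late or forgotten.

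**Conclusion.** The point holds as a low-severity improvement. Time zero for both CGM index values is an unchecked self-report, made minutes to about 4 hours after a drink taken between 6 AM and noon, and later if a survey is missed. Timing error unrelated to true status would lower the AUC.

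How far is not known. With an error-free AUC of 0.73, three of the nine scenarios fall below 0.7: slope 1.0 with an SD of 20 minutes, and slope 1.5 with SDs of 15 and 20. At slope 0.5 the AUC stays at about 0.72 or above. With an error-free AUC of 0.83, no scenario falls below about 0.75. The slope, timing-error SD, correlation and glucose SD are all assumptions.

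It would go too far to say that the procedure makes H2 likely to fail. The direction of the effect is clear, but in most scenarios the loss is smaller than one standard error of the AUC at 32 evaluable subjects. The case for acting is that the error is avoidable at almost no cost.

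**What to change.** 1. In section 5.3.2 and the visit instructions (section 5.2), ask participants to text the study platform when they start and when they finish the drink. Use the receipt time as time zero. State in section 7.4.1 whether start or finish begins the 2 h 5 min clock; both are collected, and the plan does not say which is used.
2. First confirm that the platform accepts unprompted texts and keeps their receipt times. If it does not, tell participants to write down the clock time as they drink.
3. Keep the survey or paper log as fallback.
4. Compare each reported time with the rise on the CGM trace to flag gross errors, and report how many times came from each source.
5. Leave H1b on the logging as planned, so that the feasibility question is unchanged.

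Cost: one or two extra texts per participant, a line of instruction at the visit and a short check at analysis. Sample size, endpoints and thresholds do not change.
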